WARD - Circadian analysis

Clinicaltrials.gov identifier NCT05347784

Statistical analysis plan

Version 1.1

June 9th 2023

Method

Patients

This analysis is a part of the Wireless Assessment of Respiratory and circulatory Distress (WARD) project.

The study is a nested case-control study, using patient vital sign data from 3 previous observational cohort studies of postoperative patients.

Clinicaltrials.gov identifiers:

- NCT03491137 (n=491)
- NCT04473001 (n=70)
- NCT04628858 (n=40)

All patients in the studies above have had the following vital signs recorded:

- Heart rate (HR)
- Respiration frequency (RF)
- Peripheral arterial oxygen saturation (SpO₂)
- Blood pressure (BP).

All values except BP have been recorded continuously with a 1-minute sampling rate. BP was recorded every 30 minutes during the daytime and every 60 minutes during the night.

Manual intermittent vital sign measurements were collected from electronic health records for study NCT03491137, and National Early Warning Score values will be calculated from these.

Outcomes

The primary outcome defining the case population is patients that have any postoperative serious adverse event (SAE) occurring from the start of vital sign monitoring in the ward, and up to 24 hours after vital sign monitoring. The control population will be the patients that have no recorded postoperative SAE up to 30 days after surgery. For patients with several outcomes, only measurements in the 24-hour period

preceding the first SAE were chosen for analysis. We also censored the last hour before an outcome, as this time is expected to represent the delay between clinical suspicion and confirmation by a diagnostic test for the specific SAE. For the population with no 30-day SAE, all recorded 24-hour periods were used to calculate exposure variables.

Outcomes for all studies were assessed using a standardised manual that was constructed before outcome evaluation. The definition of an SAE was taken from good clinical practice guidelines:

“any untoward medical occurrence that at any dose: – results in death,– is life-threatening,– requires inpatient hospitalisation or prolongation of existing hospitalisation, results in persistent or significant disability/incapacity, or is a medically important event or reaction.“.

Circadian definitions

Six different ‘windows’ of circadian rhythm were defined from the literature: night-time nadir, peak-to-trough, morning activation, daytime acrophase, afternoon local minimum, and evening deactivation.

Exposures

The primary exposure is the lowest vital sign values at night-nadir, as these values are thought to represent a period of least physiologic stress, and unbiased from movement, and other voluntary activity. Secondary exposures are the lowest vital sign values at the other circadian windows. We also include manually measured NEWS values in the secondary analyses.

Analyses

We did not perform a power analysis prior to analyses due to the nested case-control design.

To avoid calculating values for circadian windows with only limited data, we introduced a minimum data condition, requiring 66 % of data for a specific window-vital sign combination.

A p-value of <0.01 was considered significant to account for multiple statistical testing.

Primary analysis

The primary analysis is descriptive

Secondary analyses

Secondary analyses were a calculation of risk ratios (RR).

For this, Youden's optimal cut-off values will be calculated for each window-vital sign combination.

Afterwards, values for each patient are split into above or below Youden's optimal cut-off point, and risk ratios will be calculated from this discrimination.

For NEWS measurements, a cut-off was defined as a total NEWS score ≥ 6 or a single-parameter score of 3.

Sensitivity analysis

We will also include calculations of fitted cosine curves to vital values, from which rhythm-adjusted mean value (MESOR) and amplitude can be calculated.

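### The vital-sign risk ratios pool three cohorts without using source study, so a cohort difference in both SAE risk and vital-sign level would enter the risk ratio

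*SAP*

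**What the plan says.** Under Patients, the SAP describes a nested case-control study "using patient vital sign data from 3 previous observational cohort studies of postoperative patients": NCT03491137 (491), NCT04473001 (70) and NCT04628858 (40). Under Outcomes, cases and controls are defined across all three, with no matching or sampling by study.

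Under Secondary analyses, "Youden's optimal cut-off values will be calculated for each window-vital sign combination", and then "values for each patient are split into above or below Youden's optimal cut-off point, and risk ratios will be calculated from this discrimination". No stratum, covariate or per-study result is named. The only sensitivity analysis is the cosine fit, which is not by study. The significance rule is: "A p-value of <0.01 was considered significant to account for multiple statistical testing".

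NEWS is the exception. Its manual measurements were collected for NCT03491137 only, and its cut-off is fixed in advance. The primary analysis is descriptive, so the RRs are the only association estimates that the SAP specifies.

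**The concern.** Source study is known for every patient and may be related both to the chance of an SAE and to the level of the vital signs. If it is related to both, a crude RR over the pooled patients mixes two contrasts: patients with different vital signs inside a cohort, which is the question, and patients from different cohorts, which is not. A window-vital sign combination with no association inside any cohort could then show an RR away from 1. A real association could also be masked if the cohort effect runs the other way.

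The Youden search can add to this. It seeks the cut-off that best separates cases from controls, and separation that only reflects cohort membership counts towards that.

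**Working it through.** The SAP gives no RR, SAE risk or sample-size calculation ("We did not perform a power analysis prior to analyses due to the nested case-control design"), so there is no planned figure to reproduce. What follows is illustration. The cohort sizes come from the SAP; all risks and exposure shares are assumed.

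**Sizes.** 491 + 70 + 40 = 601; NCT03491137 is 491/601 = 81.7%. The two small cohorts are taken together as 110. The figure 601 is an upper bound: patients whose first SAE falls after the case window but by day 30 are neither cases nor controls, and the 66% data rule removes others.

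**Formula.** Let n be cohort size, r SAE risk and e the share beyond the cut-off. With no association inside any cohort, r is the same on both sides of the cut-off, and

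crude RR = [Σ n·e·r / Σ n·e] ÷ [Σ n·(1−e)·r / Σ n·(1−e)].

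**Worked example.** Risk 15% vs 35%, exposed 30% vs 50%:
- Exposed: 147.3 + 55 = 202.3 patients; cases 22.095 + 19.25 = 41.345; risk 20.4%.
- Unexposed: 343.7 + 55 = 398.7 patients; cases 51.555 + 19.25 = 70.805; risk 17.8%.
- Crude RR = 0.2044/0.1776 = 1.15.

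**Other scenarios** (491 vs 110, true within-cohort RR 1.00):

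| Risk | Exposed | Risk if exposed / unexposed | Crude RR |
|---|---|---|---|
| 20% vs 20% | 30% vs 60% | 20% / 20% | 1.00 |
| 20% vs 30% | 50% vs 50% | equal | 1.00 |
| 20% vs 25% | 40% vs 50% | 53.03/251.4, 72.67/349.6 | 1.015 |
| 20% vs 30% | 40% vs 60% | 59.08/262.4, 72.12/338.6 | 1.06 |
| 15% vs 35% | 30% vs 70% | 49.045/224.3, 63.105/376.7 | 1.31 |
| 20% vs 10% | 30% vs 60% | 36.06/213.3, 73.14/387.7 | 0.90 |
| 20% vs 10% | 30% vs 70% | 37.16/224.3, 72.04/376.7 | 0.87 |

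The first two rows show that risk and exposure share must both differ before there is any bias.

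**Mantel-Haenszel.** RR = Σ(A·n0/n) / Σ(C·n1/n), where A and C are exposed and unexposed cases and n1 and n0 are exposed and unexposed patients. In the worked example the 491 give 22.095 × 343.7/491 = 15.47 in the numerator and 51.555 × 147.3/491 = 15.47 in the denominator. The 110 give 19.25 × 55/110 = 9.625 in both. The RR is 25.09/25.09 = 1.00, and it is 1.00 in every other row.

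**Simulation** (cohorts of 491, 70 and 40, no within-cohort association, test at 0.01, two-sided assumed):
- Fixed median cut-off: the stratified test rejected in 0.4% to 1.1% of runs.
- Youden cut-off, no cohort difference: the crude test rejected in 6.7% of runs when the search ran in one direction, and in about 12% to 13.5% when it ran in both.
- Youden cut-off, risk 15% vs 35%: stratifying lowered rejection from 24% to 12% with a 0.5 SD shift in the vital sign, and from 50% to 9% with a 1.0 SD shift. The median RR still stood at about 1.3 to 1.5, because of the same-data cut-off.
- Youden cut-off, risk 15% vs 20% and a 0.2 SD shift: the crude test rejected in 12.9% of runs, against 13.5% with no cohort difference.

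**The case against.** The strongest objection is that the premise is not shown. The SAP reports neither SAE risk nor vital-sign level by cohort. What it does report points to a shared design: one project, postoperative patients, the same vital signs at the same sampling rates, and one outcome manual for all studies. With 82% of patients in one cohort, modest differences move the RR little and add almost no false positives. The RRs are also secondary, and the absence of stratification is read from silence in a short document.

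Most of this stands, and it limits the size of the point. It does not remove it. A common manual makes SAE ascertainment alike but says nothing about case mix or baseline risk. The SAP does state how the RR is computed, and source study is not part of that.

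A reader might infer that every test rests on the merged 601 patients. The documents do not support that: the NEWS RR uses one cohort with a fixed cut-off, and 601 is a ceiling.

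A reader might also infer that stratifying would bring the planned RRs back to 1.00 when there is no association. That holds for a cut-off fixed in advance, not for a Youden cut-off chosen on the same data.

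**Conclusion.** The point holds in a conditional form. The vital-sign RRs are specified as crude comparisons across three pooled cohorts, and nothing in the SAP uses source study. If SAE risk and vital-sign level both differ by cohort, the crude RR is biased for the within-cohort RR: about 1.015 to 1.06 under modest assumed differences, 1.15 to 1.31 under large ones, and 0.87 to 0.90 when the differences run in opposite directions.

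The stronger reading, that the cohorts do differ and the RRs will therefore be wrong, is not supported, because the SAP gives no cohort-specific figures. Nor should the whole of the 24% and 50% crude rejection rates be put down to pooling: part of each is cut-off optimism, which occurs with no cohort difference at all. This is a worthwhile improvement to a secondary analysis, not a demonstrated error in a result.

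**What to change.** In Secondary analyses, define the vital-sign RR as a Mantel-Haenszel RR stratified by source study, with its confidence interval and test. State in advance that the strata become 491 versus the two small cohorts combined if cases are sparse. Report the NCT03491137-only RR beside it as a sensitivity analysis; this also gives the NEWS RR a comparison from the same source study.

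A cohort-stratified ROC for choosing the cut-off is optional. At an assumed 15% risk the small cohorts would hold about 0.15 × 40 = 6 and 0.15 × 70 = 10.5 cases, and fewer after the 66% rule.

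The cost is a short change of wording and a few lines of code, with no new data. The downside is slightly wider intervals. The change does not deal with the cut-off being chosen and tested on the same patients, which needs its own remedy.

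### Controls must be free of an SAE from surgery, but the case clock starts only at ward monitoring, so an SAE before monitoring can occur only among analysed cases

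*SAP*

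**What the plan says.** The SAP's Outcomes section sets two different clocks.

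- **Cases** are patients with "any postoperative serious adverse event (SAE) occurring from the start of vital sign monitoring in the ward", until 24 hours after monitoring. No sentence says what happens to a patient who already had an SAE between surgery and the start of monitoring.
- **Controls** are defined from surgery: "The control population will be the patients that have no recorded postoperative SAE up to 30 days after surgery". This covers the time before monitoring.

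For patients with more than one outcome, only measurements in the 24 hours "preceding the first SAE were chosen for analysis". The SAP does not say whether first is counted from surgery or from the start of monitoring. For controls, the rule is: "For the population with no 30-day SAE, all recorded 24-hour periods were used to calculate exposure variables".

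Under Exposures, "The primary exposure is the lowest vital sign values at night-nadir". The primary analysis is descriptive. Under Secondary analyses, each window and vital sign is split at its Youden cut-off and "risk ratios will be calculated from this discrimination". Neither these analyses nor the sensitivity analysis (fitted cosine curves) excludes, stratifies or adjusts for an earlier SAE.

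**The concern.** Take a patient with an SAE after surgery but before ward monitoring. If a second SAE follows in the case window, the case definition admits the patient. If none follows, the control definition shuts the patient out. An earlier complication is therefore possible among analysed cases and impossible among analysed controls.

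Such a patient's monitored vital signs are recorded after the earlier event and may still reflect it. In that case part of any difference between the groups, and part of any risk ratio, would describe the aftermath of a known SAE and not the state of the patient before a new one.

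This also works against the SAP's own aims. It drops the last hour before an outcome so that an event already under way does not colour the exposure. It chooses the night nadir as a time of low physiological stress. Values recorded after an earlier complication undercut both aims, and in one group only.

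**Working it through.** The SAP states no figure on this point, so there is none to reproduce. The check has two parts.

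**1. Who enters which group**, taking the first SAE as the first in the case window:

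| SAE between surgery and monitoring | SAE in case window | Other SAE by day 30 | Group |
|---|---|---|---|
| Yes | Yes | Any | Case |
| Yes | No | Any | Neither |
| No | Yes | Any | Case |
| No | No | Yes | Neither |
| No | No | No | Control |

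An earlier SAE appears in the first two rows only. One of these is a case row and the other leaves the analysis.

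**2. How large the effect could be.** None of the inputs below is in the SAP; all are assumptions.

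- There is no true link between the vital sign and the later SAE.
- The vital sign is standard normal, oriented so that higher is more adverse.
- A share f of cases had an SAE before monitoring (5%, 10% or 20%). Among controls the share is 0 by definition.
- An earlier SAE shifts the value by d = 0.5 or 1.0 SD in the adverse direction.
- Cases form a share π = 20% or 30% of analysed patients.

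Write T(x) for the upper-tail normal probability. At cut-off c:

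- Controls beyond the cut-off: p = T(c)
- Cases beyond the cut-off: s = (1 − f)·T(c) + f·T(c − d)
- Youden index: s − p = f·[T(c − d) − T(c)], which is largest at c = d/2
- RR = [πs / (πs + (1 − π)p)] ÷ [π(1 − s) / (π(1 − s) + (1 − π)(1 − p))]

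Upper end (π = 0.20, f = 0.20, d = 1.0, so c = 0.5):

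- p = 0.3085
- s = 0.80 × 0.3085 + 0.20 × 0.6915 = 0.3851
- Risk beyond the cut-off = 0.0770 / (0.0770 + 0.2468) = 0.2378
- Risk below it = 0.1230 / (0.1230 + 0.5532) = 0.1819
- RR = 0.2378 / 0.1819 = 1.31

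Lower end (π = 0.30, f = 0.05, d = 0.5, so c = 0.25):

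- p = 0.4013
- s = 0.95 × 0.4013 + 0.05 × 0.5987 = 0.4112
- Risk beyond the cut-off = 0.1234 / (0.1234 + 0.2809) = 0.3051
- Risk below it = 0.1766 / (0.1766 + 0.4191) = 0.2965
- RR = 0.3051 / 0.2965 = 1.03

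All combinations:

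| f | π = 20%, d = 0.5 | π = 20%, d = 1.0 | π = 30%, d = 0.5 | π = 30%, d = 1.0 |
|---|---|---|---|---|
| 5% | 1.033 | 1.073 | 1.029 | 1.063 |
| 10% | 1.067 | 1.148 | 1.059 | 1.128 |
| 20% | 1.138 | 1.308 | 1.120 | 1.263 |

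With f = 0, s equals p at every cut-off and the risk ratio is 1.00. That is the situation if cases must also be free of an SAE before monitoring.

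**The case against.** The strongest reply is that the bias depends on one reading. If the first SAE means the first since surgery, a patient with an SAE before monitoring has no monitored 24 hours before it, fails the 66% minimum data condition and drops out. The bias is then zero. This stands as a limit on the point. But the SAP does not say so, and counting from surgery sits badly with an outcome defined from the start of monitoring. Two analysts could build different case groups from the same sentence.

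Second, such patients may not exist. The entry rules of the three source cohorts, and the interval between surgery and monitoring, are not in this document. Those rules may already remove early complications. This also stands. A reader might take the SAP's reference to patients with several outcomes as evidence that such patients were seen. It is not: the outcome is defined within the case window, so that sentence most naturally means several events within it.

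Third, the primary analysis is descriptive and the SAP does not call the vital signs predictors. That is true. The reading as a risk marker comes from the exposure period before the event and from the secondary risk ratios. A descriptive contrast between the two groups is still affected.

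Finally, a reader might infer that the groups as defined are biased beyond repair. They are not: restricting the cases to those without an earlier SAE removes the asymmetry.

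**Conclusion.** The two definitions differ in eligibility, and on the natural reading of the first SAE they let vital signs recorded after an earlier complication into the case group only. Nothing in the planned analyses corrects for this. If the earlier SAE moves the vital sign in the adverse direction, the descriptive contrast and the risk ratios can be pushed away from the null.

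The size is unknown. The range of roughly 1.03-1.31 for a null risk ratio of 1.00 rests on the assumed shares, shifts and case fraction. At a 5% share it is only about 1.03-1.07. A reader might infer that the planned results are shown to be biased. The document does not support that, because it neither counts such patients nor shows that there are any. What it does show is a rule that admits the bias and a wording of the first SAE that leaves the matter open. It should be corrected because the correction is simple and cheap.

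**What to change.** In the Outcomes section:

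1. Apply one entry condition to both groups: no SAE between surgery and the start of ward monitoring.
2. Define the index event as the patient's first postoperative SAE, falling between the start of monitoring and 24 hours after it. This also settles what the first SAE is counted from.
3. Report how many cases the condition removes.
4. Add a sensitivity analysis that keeps those cases, with exposure taken from the 24 hours before their first SAE in the case window.

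The cost is a few sentences. The SAE records needed run from surgery onward, and the control definition already requires them. The downside is the loss of any affected cases from the main analysis. If the source cohorts already exclude such patients, or the count is zero, one sentence saying so closes the matter.

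### Read literally, the SAP cuts the last hour out of a case's 24-hour look-back without replacing it, so cases have 23 hours against controls' 24 and some lose part of the night-nadir window

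*SAP*

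**What the plan says.** Three statements under Outcomes in the SAP bear on this.

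- Case look-back: "For patients with several outcomes, only measurements in the 24-hour period", continuing "preceding the first SAE were chosen for analysis".
- Removal of the end of that period: "We also censored the last hour before an outcome". The reason given is the lag between suspecting an event and confirming it.
- Controls: "For the population with no 30-day SAE, all recorded 24-hour periods were used to calculate exposure variables". No hour is removed.

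Under Exposures: "The primary exposure is the lowest vital sign values at night-nadir". Under Analyses, a minimum-data condition applies, "requiring 66 % of data for a specific window-vital sign combination". The clock times and lengths of the six windows are not given. Nor does the SAP say whether parts of a window from two different nights may be joined.

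**The concern.** For an SAE at time T, the case sentences leave T−24 h to T−1 h, which is 23 hours. The clock hour just before the SAE is gone. The same clock hour a day earlier (T−25 h to T−24 h) lies just outside the look-back, so nothing replaces it. A control's 24-hour period contains every clock minute once.

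This matters because each exposure is a minimum within a fixed clock window. If the missing hour overlaps the night-nadir window, the primary exposure is shortened in that case but in no control. Two consequences are possible:

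- The 66 % rule may treat equally well recorded patients differently according to the clock time of their SAE.
- A minimum over fewer readings tends to be higher, so affected case values may drift upward for reasons unrelated to physiology.

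The same values feed the Youden cut-offs and risk ratios, and the other five windows are open to the same cut.

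**Working it through.** The SAP states no power calculation or event count, so there is no figure of its own to reproduce. The check is interval arithmetic.

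**Inputs from the SAP:** a 24 h look-back, 1 h removed, the 66 % rule, 1-minute sampling of HR, RF and SpO₂, and hourly BP at night. **Assumptions:** SAE clock time uniform over 24 h; window length L shown for 2, 3 and 4 h; both case sentences apply to every case; the censored hour was recorded.

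**Length.** 24 − 1 = 23 h against 24 h per control period, or 1/24 = 4.2 % less.

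**Cases touched.** The hour [T−1, T] overlaps the window when T lies inside it or up to 1 h after it. The share is (L+1)/24.

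**Failing the 66 % rule when both nights may be pooled.** With complete data, the rule is breached when the overlap exceeds 0.34L. A one-hour cut can do this only if 0.34L < 1, so L < 1/0.34 = 2.94 h. For L = 2 h the breach needs an overlap above 0.68 h, giving (2 + 1 − 2 × 0.68)/24 = 1.64/24 = 6.8 % of cases. At L = 3 h the lowest coverage is 120/180 = 66.7 %, which just passes.

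**Failing when the window must come from one night.** Let the SAE fall x hours after the window opens.

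- As written, the current night covers x−1 hours of the window and the previous night L−x. Both fall short of 66 % when 0.34L < x < 0.66L + 1, so the share is (0.32L + 1)/24.
- With a look-back of 25 h to 1 h, the previous night covers L−x+1. Failure needs 0.34L + 1 < x < 0.66L + 1, so the share is 0.32L/24.

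| L | Touched | Lowest pooled coverage | Below 66 %, pooled, complete data | Below 66 %, one night, as written | Below 66 %, one night, look-back moved |
|---|---|---|---|---|---|
| 2 h | 3/24 = 12.5 % | 50 % | 6.8 % | 1.64/24 = 6.8 % | 0.64/24 = 2.7 % |
| 3 h | 4/24 = 16.7 % | 66.7 % | 0 % | 1.96/24 = 8.2 % | 0.96/24 = 4.0 % |
| 4 h | 5/24 = 20.8 % | 75 % | 0 % | 2.28/24 = 9.5 % | 1.28/24 = 5.3 % |

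With the look-back moved and pooling allowed, the loss is 0 % for any L, provided the extra hour was recorded.

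**Other missing data, pooled.** When the whole hour falls inside the window, the further missingness that tips a case below 66 % is 1 − 0.66/(1 − 1/L). This is 1 % at L = 3 h and 12 % at L = 4 h, against 34 % without the cut. The result is sensitive to completeness: at L = 4 h and 85 % complete, 13.4 % of cases fail; at 90 % or better, none do.

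**Effect on the minimum.** Take night BP with three hourly readings, treated as independent and normal. The expected minimum is −0.846 SD for three readings and −0.565 SD for two, a rise of 0.28 SD. At most 16.7 % of cases are affected at L = 3 h, so the case mean moves by no more than 0.28 × 0.167 ≈ 0.05 SD.

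**The case against.** The strongest reply is that the text never says the start of the look-back stayed at 24 h. A 24-hour period ending an hour before the SAE may be what was done. That is possible, but it is not what is written: the censoring is introduced as a further step, and no 25 h limit appears. If the shifted period was used, the sentence still needs correcting.

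Second, the 24-hour limit is worded only for patients with several outcomes. For a case with one SAE no limit is stated, and the same clock hour a day earlier might be included. This stands. The claim of 23 hours for every case rests on reading the limit as general.

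Third, a reader might infer that cases with night-time SAEs are systematically dropped from the primary exposure, or that the case-control comparison is materially biased. The SAP does not support either. Dropping depends on a window length it does not give, on completeness, or on a one-night rule it does not state. With pooled, complete data it is 0 % at L of 3 h or more. The 0.05 SD shift is an upper figure that shrinks when serial readings are correlated, it concerns BP only, and the primary analysis is descriptive.

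Fourth, uniform SAE times are an assumption, since confirmation by a test need not be spread evenly over the day. Also, for an SAE more than an hour after monitoring ended, the censored hour holds no recordings and its removal costs nothing. Both points stand.

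Finally, other asymmetries may be larger: controls may contribute several periods, and a case whose SAE follows the end of monitoring may have few recorded hours in the look-back. That lowers the priority of this point but does not remove it. The reason given for the censoring justifies leaving out the last hour; it does not justify leaving that hour unreplaced.

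**Conclusion.** The point holds as a modest, avoidable asymmetry. Under the literal reading applied to all cases, some cases lose up to an hour of the primary-exposure window where that hour was recorded, and no control does. How many is unknown without the window times; the 12.5 % to 20.8 % rests on uniform SAE times and an assumed 2 to 4 h window.

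Partial loss is the firm part. Exclusion under the 66 % rule is conditional: it needs a window under 2.94 h, other missing data, or a one-night requirement. The effect on group minima is small. Confidence is medium, because a clarification of the intended look-back could settle the matter.

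**What to change.** State for all cases, with one SAE or several, that exposure is taken from the 24 hours ending one hour before the first SAE (25 h to 1 h before it), and apply the 66 % rule to that period. This keeps the exclusion for diagnostic delay and restores each clock minute once, as in a control period. It also offers one more hour to cases whose SAE comes after monitoring ended.

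The SAP should also say whether window minutes from two nights may be pooled, because the benefit depends on it. With pooling the loss falls to 0 %. Without pooling, about 4.0 % (L = 3 h) or 5.3 % (L = 4 h) of cases still fall below 66 %, because an SAE inside the window splits the night. Cases with nothing recorded between 25 h and 24 h before the SAE gain nothing.

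The cost is one sentence for the look-back, a short pooling rule, and extraction of one more recorded hour per case. The downside is that up to an hour of data lies 24 to 25 h before the SAE.

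### One untested hour is removed before every type of SAE, so where suspicion came earlier than that, post-suspicion night-nadir and NEWS values may count as case exposure

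*SAP*

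**What the plan says.** Under Outcomes, a case is a patient with "any postoperative serious adverse event (SAE) occurring from the start of vital sign monitoring in the ward", up to 24 hours after monitoring ends. All SAE types are pooled under the good clinical practice definition, which runs from death to the residual category "or is a medically important event or reaction".

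For cases with several events, only measurements in the 24 hours "preceding the first SAE were chosen for analysis". Then: "We also censored the last hour before an outcome", with the reason that "this time is expected to represent the delay between clinical suspicion and confirmation by a diagnostic test for the specific SAE". For controls: "For the population with no 30-day SAE, all recorded 24-hour periods were used to calculate exposure variables".

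Under Exposures, the primary exposure is the lowest value of each vital sign in the night-nadir window, chosen as a time of little physiological stress. On NEWS the section adds: "We also include manually measured NEWS values in the secondary analyses". No separate lead time is given for NEWS.

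Under Analyses, a window counts if 66% of its data are present. The Sensitivity analysis section lists cosine fits only.

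**The concern.** The SAP recognises that data recorded once an SAE is suspected do not belong in the exposure, and the one-hour censor is its safeguard. The reason given ties the delay to the particular event, but the rule is the same for every event in a broad composite. Nothing in the SAP supports one hour for any SAE type, and no analysis shows what happens if it is too short.

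If it is too short for some SAEs, part of the retained 23 hours is time when the event was already suspected. A night nadir in that stretch no longer represents the low-stress state for which it was chosen, and a manual NEWS value from it may reflect the SAE itself. This can happen only in cases, so it bears on the case-control contrast and on the risk ratios. NEWS may be affected by a different amount: it is measured intermittently, is available from one cohort only (491 of 491 + 70 + 40 = 601 patients), and uses a fixed cut-off, whereas the window cut-offs are Youden-optimised.

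**Working it through.** The SAP has no figure to reproduce here; it states that no power analysis was done.

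**Inputs from the SAP.** Look-back 24 h; censor 1 h; minimum data 66% of a window; exposure is the lowest value in the window.

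**Assumptions, not in the SAP.** Delay from suspicion to recorded SAE time, *d* hours; night-nadir window of *L* hours; SAE times uniform over the 24-hour clock; monitoring continuing up to the event.

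**1. Post-suspicion time retained.** The retained span is 24 − 1 = 23 h, of which max(0, *d* − 1) h follow suspicion.

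| *d* | hours kept | share of 23 h |
|---|---|---|
| ≤ 1 h | 0 | 0% |
| 2 h | 1 | 4% |
| 4 h | 3 | 13% |
| 6 h | 5 | 22% |
| 12 h | 11 | 48% |

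**2. Nadir windows touched at all.** A stretch of *d* − 1 hours meets a window of *L* hours with probability (*d* − 1 + *L*)/24 for *d* > 1. For *L* = 4:

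- *d* = 3: 6/24 = 25%
- *d* = 6: 9/24 = 37.5%
- *d* = 12: 15/24 = 62.5%

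Minute-by-minute enumeration with the 66% rule applied, for *L* from 2 to 4, gives 0% at *d* = 1, 7–21% at 2 h, 16–29% at 4 h, 25–37% at 6 h and 52–62% at 12 h of usable windows.

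**3. Nadir windows wholly after suspicion.** Any overlap matters most for a sign that falls (SpO₂, BP), because a few affected readings can set the minimum. For a sign that rises (HR, RF), the minimum still comes largely from unaffected minutes unless the whole window lies after suspicion. That probability is max(0, *d* − 1 − *L*)/24. For *L* = 4:

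- *d* = 3: 0%
- *d* = 6: 1/24 = 4%
- *d* = 12: 7/24 = 29%

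A window that loses up to one of its four hours to the censor still has 3/4 = 75% of its data and passes the 66% rule. Counting those as well gives max(0, *d* − *L*)/24: 0%, 2/24 = 8% and 8/24 = 33%. Enumeration confirms both sets.

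**4. Cases left at longer leads.** With a lead of *k* hours, the retained span is *T* = 24 − *k*. The share of cases with at least 66% of a 4-hour window is (*T* + *L* − 2 × 0.66*L*)/24:

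- *k* = 6: (18 + 4 − 5.28)/24 = 16.72/24 = 70%
- *k* = 12: (12 + 4 − 5.28)/24 = 10.72/24 = 45%

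Enumeration agrees. At the one-hour censor every case keeps a usable 4-hour window, because at most one hour of the four is lost (if minutes from the two ends of the look-back are pooled by clock time).

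**The case against.** On the SAP's own expectation, the hour already removes post-suspicion data, and nothing in the document shows an SAE suspected earlier. A reader might infer that post-suspicion values definitely count as exposure. The SAP does not support that: it gives no delays, and at one hour or less the problem disappears. This objection stands, and the point is conditional.

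The SAP also does not say outright that SAE time means confirmation; that is inferred from the reason given for the censor. The outcome manual it mentions is not shown and may define timing. The SAP likewise says nothing of staff taking more observations after suspicion, so extra exposure of NEWS is plausible rather than documented.

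The overlap shares assume monitoring up to the event. Cases include SAEs up to 24 hours after monitoring. Where monitoring ended before suspicion, the wearable data contain no affected stretch whatever the delay; manual NEWS could still be affected. The shares are therefore upper figures for the wearable signs under the other assumptions. They also measure overlap, which differs from bias for signs that rise (step 3).

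A reader might further infer bias away from the null. That is not certain either. It can differ by vital sign, and treatment started on suspicion could normalise values and pull the contrast the other way.

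Finally, the primary analysis is descriptive and the SAP claims no early-warning performance. That lowers the stakes but does not remove them: the case-control description and the risk ratios both use the same retained data.

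**Conclusion.** The point holds in conditional form and is worth fixing, with medium confidence. The SAP justifies its censor by an event-specific delay, applies one unsupported hour to all SAEs, and never varies it. Where the delay is longer, night-nadir and NEWS values from after suspicion may enter the exposure of cases, with no counterpart in controls.

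The size cannot be fixed from the SAP. With a 4-hour window, uniform event times and monitoring to the event, any overlap ranges from 0% of cases (delay of one hour or less) to 62.5% (12 hours). Windows wholly after suspicion range from 0% to 29%, or 33% if windows shortened by the censor are counted. The size and direction of the resulting bias are unknown and may differ by vital sign. For wearable data the bias is zero where monitoring ended before suspicion. That the results are in fact contaminated, or the risk ratios inflated, does not follow.

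**What to change.** Keep the one-hour censor for the main result, and state in the SAP how SAE time is defined and what the hour rests on, by SAE type if it differs. Then:

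- Prespecify a lead-time sensitivity analysis that repeats the night-nadir description and the risk ratios, including NEWS, using only data ending at longer leads before the SAE. Leads of 6 and 12 hours are examples; the SAP offers no basis for a particular value.
- Report the number of cases with a valid window at each lead.
- Compare each longer-lead result with the one-hour result in the same retained cases, so that loss or selection of cases is not read as loss of the contrast.
- If the contrast shrinks in the same cases, interpret it cautiously as possibly reflecting the SAE itself. Do not make it a condition of describing values as preceding the SAE that the contrast persists: all retained case data precede the recorded event, and a contrast can fade simply because cases drop out.

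The cost is SAP wording and a rerun on existing data. The longer leads have fewer cases and wider intervals (about 70% and 45% of cases usable at 6 and 12 hours, under the assumptions in step 4), and which cases remain depends on the clock time of the SAE.
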